 - ii) The wearable group will exhibit greater desired body composition changes more rapidly than the control group
 - iii) The wearable group will less post-operative complications than the control group

4) Administrative Organization

- a) This study will solely be completed at the University of Iowa Healthcare and Clinics Department of Orthopaedics and Rehabilitation.

5) Study Design

- a) Experimental design of the study: randomized controlled trial with single blinding
- b) Study population general description
 - i) Specify total number of adult subjects, age range and percent by gender
 - (1) 90 subjects (>18 years old)
 - (2) 50% male, 50% female
 - ii) Specify total number of minor subjects (less than 18 years of age), age range and percent by gender.
 - (1) none
- c) Sample size determination and power analyses
 - i) A power analysis was performed by the orthopedic department statistician [name].
- d) Study outcomes/endpoints
 - i) Primary outcomes
 - (1) Muscle mass, body mass, and fat mass changes from baseline at 3-, 6-, 9-, and 12-months
 - ii) Secondary outcomes
 - (1) Time to achieve desired body composition changes
 - (2) Time to TJA indication
 - (3) Surgical outcomes for those that undergo TJA

6) Study Procedures

- a) Describe Subject selection procedures
 - i) Describe the sampling plan including Inclusion/Exclusion criteria (subject and disease characteristics)
 - (1) Inclusion Criteria
 - (a) Adults > 18 years
 - (b) BMI > 40kg/m2
 - (c) Presenting to arthroplasty-obesity clinic with desire for total joint arthroplasty procedure
 - (d) Owns a smartphone capable of handling iOS or Google Play apps
 - (2) Exclusion Criteria
 - (a) Has a pacemaker or other electronic pacemaker placement
 - (b) Inability to complete study protocols
 - (c) Inability to stand unsupported for 60-90 seconds
 - ii) Indicate if the study plans to enroll non-English speaking subjects. If so, specify language(s), who will translate documents, who will serve as a translator. The IRB must review and approve all translated documents.
 - (1) This group will not be enrolled
 - iii) Indicate if the study will enroll subordinates of the PI or a member of the research team.
 - (1) This group will not be enrolled
 - iv) Indicate if the study will enroll pregnant women for research on fetuses and neonates
 - (1) This group will not be enrolled

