 - (1) The patient will be identified on the clinic schedule, and they will be approached in their private clinic room. They will be asked if they are interested in participating in a study. If they agree, they will be asked the above screening questions. If they are eligible a study team member will orally review the consent form and have the participant review the written consent form. All questions will be answered.
 - iii) Specify what documents will be used in the consent process (Informed Consent Document, Consent Letter or Information Sheet, Assent Document, Verbal/Phone Script, Exempt Information Sheet, Consent Summary, Other)
 - (1) Informed consent form
 - iv) Specify if the study requires a waiver of consent OR waiver of documentation of consent. If so, provide justification.
 - (1) No waiver
 - v) Specify how long subjects can consider whether to participate AND if they can consult with other people before deciding to participate.
 - (1) They will be eligible until the end of their initial clinic visits to arthroplasty-obesity clinic
 - vi) Specify how long after subjects agree to participate before the study procedures begin.
 - (1) Immediately
- d) Describe screening procedures
 - i) Describe eligibility screening procedures before and/or after consent.
 - (1) Subjects will be asked about owning a smartphone and if they have an electronic cardiac device prior to the consent process
 - ii) Describe the screening schedule (number of visits, length of visits)
 - (1) The screening visit will be at the enrollment visit
 - iii) Indicate whether screening tests/procedures are part of standard care or done for research purposes only
 - (1) These are done per research protocol
 - iv) Specify what happens with screen failures (including any data gathered during screening)
 - (1) They will not be eligible to enroll, and no information/PHI will be recorded.
- e) Describe randomization procedures (if applicable) – Specify the randomization scheme and process.

- i) Block randomization in RedCap. Patients will be randomized at the conclusion of their clinic visit as to not influence the education they receive by the PI/provider
- f) Describe study intervention(s)
 - i) For Other types of intervention studies, describe:
 - (1) Active intervention description

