 - (a) Patients will be provided a BIA wearable (InBody BAND 2) and instructions regarding downloading smartphone app. Education regarding the device and app will be provided. In addition, they will receive the standard procedures/education provided in arthroplasty-obesity clinic
 - (2) Control group
 - (a) They will receive the standard procedures /education provided in arthroplasty-obesity clinic
- g) Describe all study assessments and activities
 - i) Provide a thorough, detailed description
 - (1) Randomization
 - (a) Once enrolled, patients will be randomized by a non-PI study member. Randomization will occur after the clinic standard education as to not be influenced based on randomization group.
 - (2) All patients
 - (a) All patients will experience a “coaching” period and be eligible for a “surgical period”. All patients (study and control) will undergo the clinic standard operating procedures of stationary BIA, hand-grip strength, and exercise and nutritional education (weight/resistance training, low carbohydrate/high protein diet) in the “coaching” period. All patients will also be advised of the goal to maintain or lose body mass, lose body fat, and gain muscle mass, which is also clinic standard operating procedure. Patients will follow-up in the clinic per standard protocol at approximately every 3 months (± 1 month). At each visit, stationary BIA, hand-grip strength, and exercise and nutritional coaching will be repeated, as is standard in clinic. All patients will be eligible to be indicated for TJA at the PI’s discretion. Per clinic procedures, patients are indicated for TJA as they achieve their body composition goals (maintain or lose body mass, lose body fat, and gain muscle mass). All patients will be instructed to not discuss their study arm (wearable or control) with the PI. Patients are eligible to enter the surgical period at any point during the coaching period. If patients feel that they meet their goals prior to they are eligible to reschedule their appointment sooner than the next visit. All patients will receive a phone call from a study team member every 1 month to assess compliance with study arm and check in on perceived progress.
 - (3) Wearable group

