 - (a) If patients are randomized the wearable group, they will be provided a wearable and instructions on installing the app and its features. They will be instructed to take BIA measurements at least weekly via the wearable. The wearable group will be instructed at the beginning of each visit to remove and keep their wearable out of sight of the PI during their visit.
 - (4) Patients who enter “Surgical” period

- (a) Patients who are indicated for TJA (at the PI's discretion) will leave the coaching period and enter the surgical period. Patients' medical record will be followed if they are indicated for TJA for post-operative outcomes such as infection, reoperation, implant failure. Surgical follow-up will occur for up to 24 months following study enrollment.
- ii) Provide a schedule of all study assessments and subject activities, including a tabular representation or timeline as applicable
 - (1) See **Table I** below
- h) Recontacting Subjects Lost to Follow Up – Indicate if the researcher will attempt to locate subjects if the research team is unable to reach them through the contact information they provided. Describe the procedures and justification for these efforts to locate subjects.
 - i) Research members will not contact the patients lost to follow, as standard clinic procedures have nursing staff contact the patients.
- i) Subject Compensation
 - i) Specify compensation method(s)
 - (1) Patients will not be compensated monetarily. Those randomized to the study cohort will be able to keep their wearable device, if desired.
 - ii) Describe the compensation plan, including amount per visit, total compensation amount, pro-rating for early withdrawal
 - (1) N/A
 - iii) Indicate whether the study will use the departmental cash handling plan or obtain approval from Accounting Services for a study-specific cash handling plan.
 - (1) N/A

7) Privacy and Confidentiality Protections

- a) Describe privacy protections – collecting data in a private space, collecting the amount and type of information you need to answer your research question(s)
 - i) Only the minimum necessary data will be collected. The data collected will be done in a private clinic room.
- b) Describe plans and justification for collecting social security number (SSN)
 - i) N/A

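### After the enrolment visit the arm is concealed only from the PI, so anyone else who coaches at months 3, 6 or 9 may know it

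*Combined protocol and SAP*

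**What the plan says.** Section 5(a) describes the design as a "randomized controlled trial with single blinding" and does not say who is blinded. The blinding has to be read from the procedures in section 6.

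- **Enrolment visit.** Section 6(e): "Patients will be randomized at the conclusion of their clinic visit as to not influence the education they receive by the PI/provider". Section 6(g)(i)(1) repeats the reasoning and adds who performs the step: "Once enrolled, patients will be randomized by a non-PI study member".
- **Later clinic visits.** Section 6(g)(i)(2) sets follow-up at about every 3 months, give or take a month, and says: "At each visit, stationary BIA, hand-grip strength, and exercise and nutritional coaching will be repeated, as is standard in clinic".
- **Concealment from then on.** Section 6(g)(i)(2): "All patients will be instructed to not discuss their study arm (wearable or control) with the PI". Section 6(g)(i)(3): at the start of each visit the wearable group is instructed "to remove and keep their wearable out of sight of the PI during their visit".
- **Contacts where the arm is known.** Section 6(g)(i)(2): "All patients will receive a phone call from a study team member every 1 month to assess compliance with study arm". Table I marks a wearable compliance check in every column from V2 to V13, which includes the clinic visits at months 3, 6 and 9. It gives no order relative to coaching and does not say who does the check.

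**The concern.** The protocol accepts that an educator who knows the arm may educate differently, and orders the enrolment visit to prevent it. It describes that educator as the PI or provider. At later visits the same kind of coaching is given to patients whose arm is already assigned, and the two remaining safeguards cover only the PI.

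Aim (i) asks whether the wristband helps when both arms receive the same standard coaching. That coaching is directed at body mass, fat and muscle, which are also the primary outcomes. A coach who knows the arm might go through home readings with wearable patients, give them more time, or make up for the missing device in controls. The arms would then differ in coaching as well as in the device. None of the analyses in section 10 could separate the two. The objectivity of the stationary BIA does not help, because this bias would act on what the patient does between visits and not on the reading.

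**Working it through.** **1. Which coaching contacts matter.** The inputs are the clinic visits in Table I, the outcome times in section 5(d) (months 3, 6, 9 and 12), and the safeguards in sections 6(e) and 6(g)(i)(2) and (3). Coaching given at a visit cannot change body composition measured at that same visit, so each contact can affect later outcomes only.

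| Clinic visit | Arm assigned before coaching? | Safeguard if the PI coaches | Safeguard if someone else coaches | Primary outcomes it can affect |
|---|---|---|---|---|
| V1, month 0 | No | Order of events | Order of events | 3, 6, 9, 12 |
| V4, month 3 | Yes | Both instructions | None stated | 6, 9, 12 |
| V7, month 6 | Yes | Both instructions | None stated | 9, 12 |
| V10, month 9 | Yes | Both instructions | None stated | 12 |
| Month 12 | Yes | Both instructions | None stated | None |

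Three contacts are therefore at issue: months 3, 6 and 9. The 3-month outcome follows only the protected enrolment coaching, so this route does not touch it. The phone visits carry no clinic-education mark in Table I and are not counted. The last clinic-education mark, as the table reads in the extracted text, could belong to V13 or to the surgical column. The count does not depend on which, because month-12 coaching affects no primary outcome.

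**2. Whether a coach other than the PI could learn the arm.** Some staff know it: a non-PI member randomizes, and a team member makes the monthly compliance calls. Whoever tells wearable patients to hide the band probably knows it too. Nothing in section 6 keeps these people from coaching, and nothing requires the clinic-visit compliance check to follow coaching or its result to be withheld from the coach. A patient who obeys both instructions to the letter may still tell a non-PI coach which arm they are in.

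**3. Whether the plan's figures give a size.** Section 10(b) states 44 per arm, 80% power, difference 1.676, SD 3.610, 5 measurements, correlation 0.500 and alpha 0.050. For a time-averaged difference under compound symmetry:

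- effective SD = 3.610 × √[(1 + 4 × 0.5)/5] = 2.796
- n per arm = 2 × (1.960 + 0.842)² × 2.796² / 1.676² = 43.7, rounded up to 44
- SE at 44 per arm = 2.796 × √(2/44) = 0.596
- power = Φ(1.676/0.596 − 1.960) = 80.3%

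The stated figure reproduces with a two-sided test. It does not size the bias: no unit or outcome is attached to 1.676, and no document says how far coaching might differ between arms or how often a non-PI person coaches.

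**The case against.** The strongest reply is that the second coach is unproven. The only hint is the compound term in "as to not influence the education they receive by the PI/provider", which may mean one person or two. Indication for surgery is left to the PI, so the PI may well run the follow-up visits. If the PI gives all the coaching, both instructions apply and the main route closes. This stands, and it makes the point conditional. A reader might infer that someone other than the PI does coach at follow-up; no section says so.

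The reply has other parts that also stand:

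- The band is to be taken off at the start of the visit, which partly hides it from everyone in the room.
- Coaching is clinic standard procedure with named content, so it is not free-form, although no script is specified.
- Patients know their arm and may mention home readings to any coach, so blinding cannot be complete.
- A reader might extend the point to staff who run the stationary BIA or the grip test. Grip strength is not a listed outcome, BIA is an instrument reading, and no route is evident by which an operator's knowledge alone would change the result.

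None of this answers the gap itself. The protocol treats the educator's knowledge of the arm as a threat at enrolment, then words the later safeguards for one person without saying that this person does all the coaching.

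**Conclusion.** The point holds as a low-cost improvement. After the enrolment visit, concealment covers only the PI, and the clinic-visit compliance check has no stated order relative to coaching. If anyone else coaches at month 3, 6 or 9, that person may know the arm, and coaching that differs by arm could bias the 6-, 9- and 12-month primary outcomes in either direction.

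This rests on two assumptions the documents leave open: that a non-PI person does some follow-up coaching, and that knowing the arm would change what that person does. The protocol's own reason for the timing of randomization supports the second; nothing settles the first.

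Two stronger readings are not supported. A reader might count four of the five coaching contacts as exposed, but only three can affect a primary outcome. A reader might also express the bias as a percentage of 1.676, but any such figure would be an assumed amount divided by a difference with no stated unit or outcome. The size is unknown.

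**What to change.** - In sections 6(g)(i)(2) and (3), extend both instructions, on not discussing the arm and on keeping the band out of sight, from *the PI* to *the PI and anyone who delivers exercise or nutritional coaching*.
- State that at clinic visits the wearable compliance check takes place after coaching, is done by a non-PI study member who does not coach that patient, and that its result is not passed to the coach.

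The cost is a wording change to instructions patients already receive, and a set order of tasks within the visit. If one person now both coaches and handles tasks that reveal the arm, those tasks must be divided among existing staff. The documents do not show how easy that would be. Blinding will remain imperfect, because patients may still mention their home readings. The change should be in place before follow-up coaching begins, since coaching already given with the arm known cannot be corrected afterwards.

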Protocol Title: Wearable Bioimpedance Analyzer for Tracking Body Composition Changes: A Randomized Controlled Trial

Protocol Version: 1.1

Protocol Date: 8/1/22

Principal Investigator: [name], PhD

Research Team: [name], [name], [name]

1) Abstract

- a) Obesity, namely at body mass index (BMI) levels exceeding $40\text{kg}/\text{m}^2$ (class III obesity), is a risk factor for many diseases including osteoarthritis (OA). In arthroplasty, patients in this population frequently present for and are turned away from surgical intervention. Subsequently, efforts are made to decrease BMI through simple weight loss, yet these have been suggested as ineffective and counterproductive. Furthermore, simple weight loss may include muscle mass loss, which is an additional risk factor for surgery. In our clinic, efforts have been made to encourage muscle mass gain and body fat loss over simple weight loss where progress has been tracked through stationary, multi-frequency bioimpedance analysis (BIA). BIA is a readily available technology offered to industry and consumers, and BIA has recently been incorporated into wearable devices. In our department, a novel clinic aimed at holistically serving the osteoarthritic-class III obese population for controlled and monitored weight loss through BIA.

This study, a randomized controlled trial, aims to recruit adult patients with class III obesity presenting to the arthroplasty-obesity clinic. While all patients will receive individual body composition coaching to increase muscle mass and decrease body fat mass, they will be randomized to one of two cohorts: the study group will receive a wearable BIA wristband (InBody BAND 2) and instruction on its use in addition to the standard coaching, and the control group will only receive the standard coaching.

This study aims to identify if the use of a wearable BIA wristband aids in the desired body composition changes. In addition, this study aims to quantify the body composition changes exhibited by each cohort. Finally, this study aims to track surgical outcomes for those patients that are indicated for total joint arthroplasty.

2) Background and Significance/Preliminary Studies

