- a) Obesity is a well-known epidemic in the US with prevalence nearing 40%. [1] Obesity is a risk factor for a myriad of disease states including osteoarthritis (OA) due to increased load on the weightbearing joints. Therefore, patients with obesity, and namely those with body mass index (BMI) approaching $>40\text{kg}/\text{m}^2$ (class III obesity), suffer from OA disproportionately compared to their non-obese peers. [2] As this population frequently reports to arthroplasty clinics, studies have identified increased rates of post-operative complications following total joint arthroplasty (TJA) specifically in the class III obese population. [2-5] To combat this increased risk, arthroplasty surgeons traditionally have excluded this population from their surgical practice or encouraged their patients to lose weight in order for their BMI to drop below $40\text{kg}/\text{m}^2$; however, these practices have been recently questioned. [6-8]

With the validity of lowering BMI to improve TJA outcomes being questioned, studies have made efforts to identify more patient-specific factors such as body composition. Body composition can be identified through several modalities including anthropomorphic measurements, DEXA, MRI, and CT. [9-11] In addition, bioimpedance

analysis (BIA) offers rapid, accurate, and non-invasive assessment without the use of ionizing radiation. [9, 12, 13] BIA can be completed through multiple devices including a stationary, scale-like device, a portable ECG-like device, or even wearable wristbands.

Our group has conducted numerous studies focusing on body composition in arthroplasty patients, including changes they experience following surgery and pre-operative risk identification. By employing both clinic-based and home-based assessments more frequently than patients would normally have, this study aims to identify any benefit, if any, a wearable BIA device serves in an obese-arthroplasty population.

3) Study Aims

- a) Aims:
 - i) To identify if the use of a wearable BIA wristband aids in the desired body composition changes (body mass loss, fat mass loss, skeletal muscle mass gain)
 - ii) To quantify the body composition changes exhibited by each cohort
 - iii) To track surgical outcomes for those patients that are indicated for total joint arthroplasty
- b) Hypotheses:
 - i) The wearable group will exhibit the desired body composition changes more rapidly than the control group

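### Section 10 a) has no rule for patients who leave coaching on reaching goals that are also the primary outcomes, so comparing those still measured is in general biased at months 6 to 12 if BIA stops at indication

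*Combined protocol and SAP*

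**What the plan says.** - Primary outcomes (section 5 d) i): "Muscle mass, body mass, and fat mass changes from baseline at 3-, 6-, 9-, and 12-months". One secondary outcome is "Time to TJA indication".
- Exit from coaching (section 6 g) i) (2)): "patients are indicated for TJA as they achieve their body composition goals", these being to "maintain or lose body mass, lose body fat, and gain muscle mass". Indication is at the PI's discretion, and no numeric goal is given. Patients who think they have met their goals need not wait: "they are eligible to reschedule their appointment sooner than the next visit".
- After indication (section 6 g) i) (4)): patients "will leave the coaching period and enter the surgical period". The text there describes only medical-record follow-up for post-operative outcomes. Stationary BIA is described under coaching. Footnote a of Table I allows exit at any time point.
- Hypothesis (section 3 b) i): "The wearable group will exhibit the desired body composition changes more rapidly than the control group".
- Analysis (section 10 a): a noninferiority comparison at each time point, with ANOVA and ANCOVA named. The template prompt asks for an intent-to-treat plan; the three items beneath it give no analysis set and no handling of leavers.
- Sample size (section 10 b): 44 per arm, 80% power, difference 1.676, SD 3.610, five repeated measurements, compound symmetry with correlation 0.500, alpha 0.050.

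**The concern.** This is not ordinary dropout. Patients stop being measured because they did well on the quantities being compared. The plan's own hypothesis has the wearable arm reaching goals faster, so it implies earlier exits in that arm. Section 10 a) does not say that only patients still measured will be compared, but a visit-wise ANOVA or ANCOVA does exactly that unless something else is specified.

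Three of the four primary time points are exposed. An outcome the wearable improves can look less improved. An outcome it does not affect can drift against it. The latter matters most for muscle, because the abstract warns that "simple weight loss may include muscle mass loss, which is an additional risk factor for surgery".

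An effect on a goal is not required. The wearable arm alone is told to take BIA at home at least weekly (section 6 g) i) (3)), and any patient may come early. The device could therefore change how often or how early patients exit without changing body composition. Month 3 is protected only if the BIA taken at an early exit visit is kept.

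**Working it through.** **1. The plan's own figure.** The SD of a mean of five compound-symmetric measurements is 3.610 × √((1 + 4×0.5)/5) = 2.796. Then n = 2 × (1.960 + 0.842)² × 2.796² / 1.676² = 43.7, so 44 per arm (power 80.3%). The stated size therefore reproduces as a two-sided test of a time-averaged difference with all measurements complete. A single-visit comparison with all 44 measured has SE 3.610 × √(2/44) = 0.77 and power Φ(1.676/0.77 − 1.96) = 58.6%. Sections 10 a) and 10 b) thus describe different contrasts.

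The documents do not say which five measurements are meant; baseline plus four visits is the natural reading. Averaging only the four follow-up changes gives SD 3.610 × √((1 + 3×0.5)/4) = 2.854 and 46 per arm. Adjusting for baseline lowers that SD to 3.610 × √(0.625 − 0.25) = 2.211.

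**2. Distribution of change.** With correlation 0.5, change from baseline has variance 2 × 3.610² × (1 − 0.5) = 3.610², and changes at two visits correlate 0.5.

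**3. Mechanism in closed form (one goal, month 6).** Suppose patients whose month-3 change exceeds c leave with probability q. With mean change μ and a = (c − μ)/3.610, the mean month-6 change among those remaining is μ − 0.5 × 3.610 × qφ(a) / [1 − q(1 − Φ(a))].

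- *Effect 1.676, q = 1, c exceeded by 20% of controls (assumed).* Control: a = 0.842, shift −1.805 × 0.2800/0.8000 = −0.632. Wearable: a = 0.842 − 1.676/3.610 = 0.377, shift −1.805 × 0.3715/0.6470 = −1.036. Observed difference: 1.676 − 1.036 + 0.632 = 1.27.
- *No effect, c = 0, q = 0.50 (wearable) against 0.25 (control).* Shifts: −1.805 × 0.5 × 0.3989/0.75 = −0.480 and −1.805 × 0.25 × 0.3989/0.875 = −0.206. Observed difference: −0.27 where the truth is 0.

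**4. One goal, simulated (1,000,000 per arm, flat control trend, constant effect).** Difference in change among those still measured:

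| Exit rule (assumed) | Truth | Month 6 | Month 9 | Month 12 |
|---|---|---|---|---|
| Certain exit, 20% of controls over c | 1.676 | 1.26 | 1.09 | 0.97 |
| Any improvement, q = 0.5 | 1.676 | 1.67 | 1.61 | 1.52 |
| Any improvement, q = 0.25 | 1.676 | 1.69 | 1.70 | 1.69 |
| No effect, q equal (0.5) | 0 | 0.02 | 0.01 | 0.01 |
| No effect, q = 0.50 against 0.25 | 0 | −0.28 | −0.52 | −0.72 |

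A compound-symmetry likelihood estimate on all observed visits returned 1.67 to 1.69 where the truth was 1.676, and −0.01 to 0.02 where it was 0. Exit there depends only on measured values, apart from chance.

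**5. All three goals required for exit (closest to section 6), month 12.** Thresholds of 0 to 0.5 SD, control trends, cross-outcome correlations and exit probabilities are assumptions; each outcome is scaled so that positive is desired.

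- Wearable improves all three by 1.676: difference in change from about 0.9 (certain exit) to about 1.6 (probability 0.25); baseline-adjusted ANCOVA about 1.25 to 1.65.
- Wearable improves mass and fat only: muscle, with no true effect, shifts by up to about −0.7 (ANCOVA about −0.4). At probability 0.25 (flat trend) it is −0.13 to −0.06.
- No effect on any goal, exit probability 1 (wearable) against 0.5 (control), correlation 0 to 0.6: about −0.2 to −0.6.
- Wearable worse by 1.676 on all three: looks worse by only 1.00 to 1.66.
- Likelihood model through the exit visit: 1.62 to 1.73 on affected outcomes for on-schedule visits. With early visits between scheduled ones it gives 1.52 to 1.84 if the early BIA is assigned to the next visit, and 1.30 to 1.74 if it is dropped.

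**The case against.** - *The sample size implies a repeated-measures analysis.* Perhaps, and such a model by likelihood would be close to unbiased here. But section 10 b) is a power statement and section 10 a) names no such model. What stands is that the two are unreconciled, not that the plan chose a restricted analysis set. A reader might infer that choice, but section 10 a) is silent on it.
- *BIA may continue after indication.* In the available text of Table I the last stationary BIA mark falls under Surgical and month 12 is blank. A column may be displaced, so this settles nothing either way. Every figure above assumes BIA stops. If it continues, values after indication still need a rule.
- *The bias may be small.* Correct. With exit probability 0.25 it is slight, and single outcomes can escape it: when only fat is affected, fat itself shows 1.57 to 1.78.
- *A false muscle disadvantage would be reported.* A reader might infer this. The documents do not support it: the illustrated shift of up to 0.7 is below one standard error (0.77 with all 44 per arm measured, larger after exits), and the ANCOVA shift is smaller.
- *Bias is judged against one estimand.* This stands. The yardstick is change had coaching continued, which the plan has not chosen. Nor is it true that every other estimand needs BIA after indication; while-in-coaching and composite estimands do not.
- *The time-to-event secondary outcomes cover it.* They treat goal achievement or indication as the event and so avoid this loss, but they do not repair the primary outcomes.

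**Conclusion.** The point holds, conditionally. If BIA stops at indication, comparing only patients still measured is in general biased at months 6 to 12 for the effect under continued coaching, when the wearable affects a goal or alters exit frequency or timing. It would be wrong to infer that the comparison is safe whenever the wearable affects no goal; it must also leave the exit process unchanged.

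The size is unknown. The documents give no exit rate and no numeric goal, leave indication to discretion, and do not name the outcome behind 1.676. The ranges in the working are illustrations that apply one SD and one correlation to all three outcomes.

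For superiority, the shrinkage on an affected goal is conservative. Under the noninferiority wording it is not, since a worse device looks closer to control. A reader might infer an inflated false-positive rate, but no margin is stated, so none can be claimed. The gap should be closed before analysis because a better method exists on data already being collected.

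**What to change.** In section 10 a):

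1. State the estimand for TJA indication. While-in-coaching or composite estimands need no BIA after indication; a treatment-policy estimand would.
2. If the target is change had coaching continued, make the primary analysis of each BIA outcome a likelihood-based repeated-measures model (arm by visit, baseline-adjusted) in all randomised patients. Use every stationary BIA up to and including the one at indication. Keep BIA from early rescheduled visits, at actual time or assigned to the next visit.
3. Name the primary contrast, for example the time-averaged arm difference, and align section 10 b) with it, including which measurements it averages.
4. Report exits by arm and visit.
5. Add a delta-adjusted missing-not-at-random sensitivity analysis by arm, because discretion may depend on more than recorded BIA.
6. Reconcile section 6 g) i) (4) with Table I on whether BIA continues after indication.

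Cost: wording and modest programming, with no new visits. The model relies on recorded BIA explaining exit (missing at random), and off-schedule visits are handled only approximately. Lost precision is not fully recovered: with all three goals affected, illustrated month-12 power is 18% to 67%, against 70% for ANCOVA with no exits.
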